#### **4.2.3 Partial Remission Rate and Duration (IRRC-assessed)**

The partial remission rate (PRR) is defined as the number of subjects with a BOR of PR according to the 2007 revised International Working Group Criteria for Malignant Lymphoma, based on IRRC assessment, divided by the number of treated subjects.

To further characterize PRR, the duration of PR will also be evaluated in subjects with objective response of PR. Duration of PR is defined as the time from first documentation of PR to the date of initial objectively documented progression as determined using the 2007 IWG criteria or death due to any cause, whichever occurs first. Censoring will be applied as per DOR definition.

#### **4.2.4 Progression Free Survival (IRRC-assessed)**

Progression free survival (PFS) is defined as the time from first dosing date to the date of the first documented progression, as determined by an IRRC according to the 2007 revised International Working Group Criteria for Malignant Lymphoma, or death due to any cause, whichever occurs first.

- Subjects who die without a reported progression will be considered to have progressed on the date of their death.
- Subjects who did not progress or die will be considered as not progressed and will be censored on the date of their last assessment.

- Subjects who did not have any on study assessments and did not die will be censored on the first dosing date.
- Subjects who started any subsequent anti-cancer therapy without a prior reported progression will be censored at the last assessment prior to initiation of the subsequent anti-cancer therapy. Stem Cell Transplant will be considered as subsequent therapy.

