The fourth secondary objective will be measured by IRRC-assessed progression free survival (PFS). It is defined as the time from first dosing date to the date of the first documented progression, as determined by an IRRC, or death due to any cause, whichever occurs first. Subjects who die without a reported progression will be considered to have progressed on the date of their death. Subjects who did not progress or die will be censored on the date of their last evaluable assessment. Subjects who did not have any on study assessments and did not die will be censored on the first dosing date. Subjects who started any subsequent anti-cancer therapy without a prior reported progression will be censored at the last evaluable assessment prior to initiation of the subsequent anti-cancer therapy.

The fifth secondary objective will be measured by investigator-assessed ORR. Investigator-assessed ORR is defined similarly as described for the primary endpoint above.

[REDACTED]

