## 4.2 Secondary Endpoints

### 4.2.1 Duration of Response (IRRC-assessed)

Duration of response (DOR) is defined as the time from first response (CR or PR) to the date of initial objectively documented progression as determined using the 2007 revised International

Working Group Criteria for Malignant Lymphoma or death due to any cause, whichever occurs first. For subjects who neither progress nor die, the DOR will be censored on the date of their last evaluable tumor assessment. Subjects who start subsequent therapy without a prior reported progression will be censored at the last evaluable tumor assessments prior to initiation of the subsequent anticancer therapy. Stem Cell Transplant will be considered as subsequent therapy. This endpoint will only be evaluated in subjects with objective response of CR or PR.

Duration of Stable Disease will also be evaluated for subjects with SD as best response. Duration of SD is defined as the time between the first dose date to the date of the first documented progression, as determined by IRRC, or death due to any cause, whichever occurs first. Subjects who neither progress nor die will be censored at the same time they will be censored for the DOR analysis.

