**Table 4.2.4-1: Censoring scheme used in primary analysis of PFS**

Situation	Date of Progression or Censoring	Outcome
No baseline tumor assessments and no death	First Dosing date	Not Progressed
No on study tumor assessments and no death	First Dosing date	Not Progressed
New anticancer treatment started without a prior reported progression per 2007 IWG criteria	Date of last tumor assessment prior or on the date of initiation of the subsequent anti-cancer therapy	Not Progressed
Clinical progression without evidence of progression per 2007 IWG criteria or No progression	Date of last tumor assessment with no documented progression	Not Progressed
Progression per 2007 IWG criteria documented between scheduled visits or at scheduled visit without prior new anticancer treatment started	Date of the first documented tumor progression per the 2007 IWG criteria	Progressed
Death without progression per 2007 IWG criteria	Date of death	Progressed

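### SAP 4.2.4 censors IRRC-assessed PFS at the last assessment where protocol 8.3.2 requires an evaluable one; if unevaluable scans count, PFS can only stay the same or rise

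*SAP*

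**What the plan says.** Protocol 8.3.2 defines the censoring of IRRC-assessed PFS twice, each time with evaluability as a condition. For subjects without an event: "Subjects who did not progress or die will be censored on the date of their last evaluable assessment". For those who start another anti-cancer treatment first: "will be censored at the last evaluable assessment prior to initiation of the subsequent anti-cancer therapy".

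SAP 4.2.4 covers the same two situations without the condition: "Subjects who did not progress or die will be considered as not progressed and will be censored on the date of their last assessment", and, for subsequent therapy, "will be censored at the last assessment prior to initiation of the subsequent anti-cancer therapy". Table 4.2.4-1 follows the SAP text, with "Date of last tumor assessment prior or on the date of initiation of the subsequent anti-cancer therapy" in the new-treatment row and "Date of last tumor assessment with no documented progression" in the row for clinical progression only or no progression.

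For DOR, SAP 4.2.1 keeps the protocol's condition: "the DOR will be censored on the date of their last evaluable tumor assessment". Duration of stable disease takes its censoring date from the DOR rule, and duration of CR and of PR do the same (SAP 4.2.2 and 4.2.3).

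Both documents send a surviving subject with no on-study assessment back to the first dosing date. In the SAP: "Subjects who did not have any on study assessments and did not die will be censored on the first dosing date". Neither says what happens when on-study scans exist but none is evaluable.

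**The concern.** Elsewhere the SAP treats evaluability as a property that a scan may lack. The response-evaluable population in 6.3.2 requires an evaluable on-study measurement, and the IRRC/investigator cross-tabulation in 7.5.1.2 keeps non-evaluable apart from not reported. A programmer could therefore reasonably let an unreadable scan set the PFS censoring date.

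Three things follow on that reading:

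- The protocol and the SAP can give different PFS results from the same data.
- For a subject whose best response is stable disease, PFS and duration of stable disease are the same interval (first dose to IRRC progression or death), yet they can carry different censoring dates.
- A subject whose only on-study scan is unreadable is credited with progression-free time up to that scan, although no evaluable scan supports it.

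The error runs in one direction, towards a more favourable curve. The only planned PFS sensitivity analysis (SAP 7.5.5.1) concerns events and assessments after subsequent therapy, so it would not show this.

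**Working it through.** The documents state no expected median, event count or power for PFS, so there is no figure of theirs to reproduce. The check has three parts.

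**1. The rules side by side**

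| Situation | Protocol 8.3.2 (PFS) | SAP 4.2.4 and Table 4.2.4-1 (PFS) | SAP 4.2.1 (DOR, duration of SD) |
|---|---|---|---|
| No progression or death | last evaluable | last | last evaluable |
| New therapy before progression | last evaluable | last | last evaluable |
| No on-study scan, alive | first dose | first dose | not stated |
| Only unevaluable scans, alive | not addressed | read literally, the last such scan | not addressed |

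**2. Direction**

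The product-limit estimate is S(t) = ∏(1 − dᵢ/nᵢ) over event times up to t. Moving a censoring date later leaves every dᵢ unchanged and can only keep or raise nᵢ. Each factor therefore stays the same or rises.

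Example on the 8-week grid (56/30.4375 = 1.84 months), with 10 subjects. There are three events at 1.84 months and one each at 3.68, 5.52 and 7.36; one subject is censored at each of the four times.

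- Original dates: 1 − 3/10 = 0.700; × 5/6 = 0.583; × 3/4 = 0.438; × 1/2 = 0.219.
- With the subjects censored at 1.84 and 3.68 each moved one scan later: 0.700; × 6/7 = 0.600; × 4/5 = 0.480; × 1/2 = 0.240.
- The median is 5.52 months both times.

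In 20,000 random data sets with censoring moved later, none gave a lower curve at any event time and none a lower median.

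**3. Size (all rates assumed)**

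From the documents: cohorts of about 90 and 30, and the scan schedule of Table 5.4.1-1 with its windows.

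Assumed:
- 5–20% of scans unevaluable, independently of one another;
- 10–30% of subjects leaving for new therapy or drop-out by 6 months;
- exponential PFS with true median 3 or 6 months, and 15% of events being deaths;
- follow-up uniform over 6–24 months;
- progression dated at the first evaluable scan.

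The SAP rule uses the last scan. The comparison rule uses the last evaluable scan, or first dose if there is none. There were 1,000 trials in each of 36 cells. Mean results for n = 90, in percent, SAP rule v comparison rule:

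| Unevaluable, leaving | 6-month PFS, true median 6 | 12-month PFS, true median 6 | 6-month PFS, true median 3 |
|---|---|---|---|
| 5%, 10% | 52.1 v 52.0 | 28.2 v 27.9 | 27.1 v 26.9 |
| 10%, 20% | 52.4 v 52.0 | 27.9 v 27.1 | 27.4 v 26.9 |
| 20%, 30% | 53.2 v 51.8 | 28.8 v 26.7 | 29.0 v 27.6 |

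- Over all cells, the mean rise at n = 90 is 0.1–1.4 points at 6 months and 0.2–2.1 at 12 months. At n = 30 it is 0.1–1.4 and 0.1–2.0.
- With 5–10% unevaluable, it is at most 0.6 and 0.9 points.
- The SAP curve was never the lower one at 6 or 12 months in any trial.
- On average 0.8–8.2 of 90 subjects (0.2–2.8 of 30) get a later censoring date.
- Against the same n = 90 trials with every scan evaluable, the SAP rule overstates 12-month PFS by 0.3–2.4 points and the comparison rule by 0.0–0.9. At 6 months the figures are 0.5–3.5 and 0.3–2.6.

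A harsher grid, with scans fixed at nominal dates, used medians of 2, 4 or 8 months, 20% or 40% of subjects censored before an event, and 10–50% of those with an unevaluable last scan. It gave mean rises of 0.1–2.7 points at 6 months and about 0.01–0.5 month in the median.

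**The case against.** The strongest reply is that the effect depends on a definition we cannot see. Neither document defines evaluability for a single scan, and both leave IRRC procedures to the IRRC charter. An unreadable scan may not yield an IRRC assessment at all, and the no-progression row of Table 4.2.4-1 can be read as needing a scan on which progression could be judged. This stands as a limit: the upward shift is conditional. It does not remove the conflict, because the SAP uses the qualifier for DOR and omits it for PFS.

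Second, part of the wording was chosen. The SAP's document history for version 2.1 records the change for censoring linked to anti-cancer treatment. That makes it an unexplained departure from the protocol, whose Revised Protocol 03 keeps the evaluable condition. The log entry does not name the no-progression rule, which carries the same wording.

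Third, the comparison rule includes a first-dose provision that the protocol does not contain. In a rerun, that provision supplied 6–22% of the 6-month rise and 2–8% of the 12-month rise, so most of the difference comes from the missing qualifier.

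Fourth, the effect is small against sampling error: the 6-month estimate had a standard deviation of 5–6 points at n = 90 and 8.5–10.4 at n = 30. The effect on the median is also unstable. It changed in 4–58% of trials of 90 in the main simulation and in up to 71% in repeat runs. The shift was usually slight with scans spread over their windows (typically 0.03–0.13 month at n = 90), but when the median moved with scans at fixed dates it was usually by a whole scan interval. These points are fair and keep the finding modest, but a difference that always favours the drug does not average out.

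**Conclusion.** The concern holds. The current protocol and SAP give different censoring rules for IRRC-assessed PFS, and the SAP's PFS rule also differs from its own rule for DOR and duration of stable disease. If an unevaluable scan counts as an assessment, the direction is a mathematical certainty: PFS stays the same or rises. The size is assumption-driven. Under the main assumptions it is about 0.1–1.4 percentage points at 6 months and 0.2–2.1 at 12 months for 90 subjects, and under the harsher grid up to 2.7 points at 6 months. No decision rule is affected. It should be corrected because it is an avoidable inconsistency that can favour only one side.

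**What to change.** - In both censoring rules of SAP 4.2.4, and in the new-treatment and no-progression rows of Table 4.2.4-1, make the censoring date the last evaluable tumor assessment, as in protocol 8.3.2 and SAP 4.2.1.
- Add that surviving subjects with no evaluable on-study assessment are censored at the first dosing date. This extends the existing first-dose rule and fills a gap in both documents.
- State, or cite from the IRRC charter, when a single scan is evaluable.
- While editing, reconcile the subsequent-therapy rule: the table admits a scan on the day new therapy starts, but the text requires one before it.

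If the sponsor intends the departure, the SAP should justify it and add a sensitivity analysis censored at the last evaluable assessment.

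The cost is SAP wording and minor programming, with no new data. PFS estimates may come out slightly less favourable.

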**Table 4.2.4-1: Censoring scheme used in primary analysis of PFS**

Situation	Date of Progression or Censoring	Outcome
No baseline tumor assessments and no death	First Dosing date	Not Progressed
No on study tumor assessments and no death	First Dosing date	Not Progressed
New anticancer treatment started without a prior reported progression per 2007 IWG criteria	Date of last tumor assessment prior or on the date of initiation of the subsequent anti-cancer therapy	Not Progressed
Clinical progression without evidence of progression per 2007 IWG criteria or No progression	Date of last tumor assessment with no documented progression	Not Progressed
Progression per 2007 IWG criteria documented between scheduled visits or at scheduled visit without prior new anticancer treatment started	Date of the first documented tumor progression per the 2007 IWG criteria	Progressed
Death without progression per 2007 IWG criteria	Date of death	Progressed

**4.2.5 Objective Response Rate (Investigator-assessed)**

Investigator-assessed ORR is defined similarly as described for the primary endpoint above (section 4.1) and will be further characterized by TTR and DOR.

[REDACTED]

[REDACTED]

[REDACTED]

[REDACTED]

[REDACTED]

[REDACTED]

[REDACTED]

[REDACTED]

## 5 SAMPLE SIZE AND POWER

The planned sample size for this study will be approximately 120 treated subjects, separated into two cohorts based on prior ASCT failure [n= approx. 90] or ASCT ineligibility [n= approx. 30].

For the ASCT-failed cohort, a modified Simon's two-stage design will be used to test the null hypothesis that the true ORR is  $\leq 20\%$  (not considered clinically compelling). In the first stage, 37 treated subjects will be accrued. If there are 8 or fewer responses in these 37 subjects, the study will be stopped. In this case, the study will be terminated in both the ASCT-failed cohort as well as the ASCT ineligible cohort. Otherwise, approximately 53 additional subjects will be accrued into the ASCT-failed cohort to target a total of 90 treated subjects. The null hypothesis will be rejected if 25 or more responses are observed in 90 treated subjects. This design yields a one-sided type I error rate of 5% and power of 90% when the true response rate is 35%. The interim stopping rule for this design is identical to Simon's "optimal" 2-stage design, thereby limiting the expected number of subjects who receive treatment when the true response rate is not of clinical value. However, the sample size at the final analysis is larger than required by Simon's optimal design in order to provide additional subjects for safety evaluation. Table 5-1 provides the probabilities of stopping at different ORR using this rule.

**Table 5-1: Operating Characteristics of Stopping Rule**

True ORR	P(early stop)
15%	0.91
20%	0.69
25%	0.40
30%	0.18
35%	0.06
40%	0.01

For the ASCT ineligible cohort, the sample size of 30 treated subjects is determined to achieve a confidence interval (CI) width around the ORR estimate with a sufficient level of precision. If the observed number of subjects with ORR is 10 (33%), the width of the exact 2-sided 95% CI is 36%

with a lower bound of 17.3%. Such an observation would provide evidence in support that the true ORR is greater than or equal to 17.3% with a Type I error rate of 5%.

## **6 STUDY PERIODS, TREATMENT REGIMENS AND POPULATIONS FOR ANALYSES**

### **6.1 Study Periods**

#### **6.1.1 Baseline Period**

Baseline evaluations or events will be defined as evaluations or events that occur before the date and time of the first dose of study treatment.

In cases where the time (onset time of event or evaluation time and dosing time) is missing or not collected, the following definitions will apply:

- Pre-treatment AEs will be defined as AEs with an onset date prior to but not including the day of the first dose of study treatment
- Baseline evaluations (laboratory tests, pulse oximetry and vital signs) will be defined as evaluations with a date on or prior to the day of first dose of study treatment

If there are multiple valid assessments, the assessment that is closest to day (and time if collected) of the first dose of study treatment will be used as the baseline in the analyses. If multiple assessments are collected at the same date (and time if collected), the assessment with the latest database entry date (and time if collected) will be considered as baseline.

#### **6.1.2 Post Baseline Period**

On-treatment AEs will be defined as AEs with an onset date-time on or after the date-time of the first dose of study treatment (or with an onset date on or after the day of first dose of study treatment if time is not collected or is missing). An AE will be counted as on-treatment if the event occurred within 30 days (or 100 days depending on analysis) of the last dose of study treatment. Refer to Core SAP.

On-treatment evaluations (laboratory tests, pulse oximetry and vital signs) will be defined as evaluations taken after the day (and time, if collected and not missing) of first dose of study treatment. An evaluation will be counted as on-treatment if it occurred within 30 days (or 100 days depending on analysis) of the last dose of study treatment. Refer to Core SAP.

### **6.2 Treatment Regimens**

All subjects will be treated with nivolumab.

### **6.3 Populations for Analyses**

#### **6.3.1 Study Cohorts**

ASCT-failed cohort: All subjects with prior ASCT (per CRF)

ASCT ineligible cohort: All subjects without prior ASCT (per CRF)

#### **6.3.2 Analysis Populations**

Within each cohort the following populations will be defined.

- **All enrolled subjects:** All subjects who signed an informed consent form and were registered into the IVRS.
- **All treated subjects:** All enrolled subjects who received at least one dose of nivolumab. This is the primary population for efficacy and safety.
- **All response evaluable subjects:** All treated subjects who have baseline and at least one on-study evaluable tumor measurement.

[REDACTED]

## 7 STATISTICAL ANALYSES

### 7.1 General Methods

Unless otherwise noted, the bulleted titles in the following subsections describe tabulations of discrete variables, by the frequency and proportion of subjects falling into each category. Percentages given in these tables will be rounded and, therefore, may not always sum to 100%. Continuous variables will be summarized using the mean, standard deviation, median, minimum and maximum values.

Time to event distribution (e.g. progression free survival, overall survival, time to response, and duration of response) will be estimated using Kaplan Meier techniques. Median survival time along with 95% CI will be constructed based on a log-log transformed CI for the survivor function  $S(t)$ . Rates at fixed time points will be derived from the Kaplan Meier estimate and corresponding confidence interval will be derived based on Greenwood formula for variance derivation and on log-log transformation applied on the survivor function  $S(t)$ .

### 7.2 Study Conduct

#### 7.2.1 Accrual

The following will be summarized on the enrolled population for the 2 cohorts separately and on the pooled population:

- Number of subjects accrued by country and investigational site
- Number of subjects accrued by month

A by subject listing of accrual will be produced.

### **7.2.2 Relevant Protocol Deviations**

The following programmable deviations will be considered as relevant protocol deviations. Non-programmable relevant eligibility and on-treatment protocol deviations, as well as significant (both programmable and non-programmable) eligibility and on-treatment protocol deviations will be reported through ClinSIGHT listings.

#### **At entrance:**

- Subjects without documented relapsed, refractory DLBCL, or transformed lymphoma (TL)
- Subject without measurable disease at baseline
- Subject with baseline ECOG >1

#### **On-Study:**

- Any concurrent antineoplastic therapy (ie, chemotherapy, hormonal therapy, immunotherapy, surgical resection of lesions, non palliative radiation therapy, or standard or investigational agents for treatment of cancer).

A summary table will be produced for the 2 cohorts separately and on the pooled population. A by subject listing will be produced.

### **7.3 Study Population**

Analyses from this section will be produced for the 2 cohorts separately and on the pooled population.

#### **7.3.1 Subject Disposition**

The total number of subjects enrolled (treated or not) will be presented along with the reason for not being treated.

Number of subjects who discontinued treatment along with corresponding reason will also be tabulated.

#### **7.3.2 Demographics and Other Baseline Characteristics**

Descriptive statistics will be summarized the following baseline characteristics for all treated subjects. All baseline presentations will identify subjects with missing measurements. Listings will also be provided.

- Age (descriptive statistics)
- Age categories (<65, ≥65 and <75, ≥ 75, ≥65)
- Gender, Race/Ethnicity
- Region (US/Canada vs. Europe vs. Rest of World)
- ECOG PS
- weight
- Smoking Status (Yes/No/Unknown)
- Initial disease diagnosis (Diffuse Large B-Cell Lymphoma, Follicular Lymphoma)

- Time from the initial diagnosis to first transplant (< 1 year, 1 - < 2 year, 2 - < 3 year, 3 - < 4 year, 4 - < 5 year, ≥ 5 year) (only for ASCT failed cohort )
- Time from the most recent transplant to first dose of nivolumab ) (< 1 year, 1 - < 2 year, 2 - < 3 year, 3 - < 4 year, 4 - < 5 year, ≥ 5 year) (only for ASCT failed cohort)
- Time from initial disease diagnosis to first dose of nivolumab (< 1 year, 1 - < 2 year, 2 - < 3 year, 3 - < 4 year, 4 - < 5 year, ≥ 5 year)
- Disease stage at initial diagnosis (Stage I-II-III-IV)
- Revised International Prognostic Index (IPI) Score (0, 1, 2, 3, 4, 5) at initial diagnosis
- Lymphoma involvement in bone marrow at baseline (Yes/No/Not Available)
- Disease diagnosis at enrollment (DLBCL/Transformed Lymphoma, Relapse/Refractory)
- All lesions (Investigator Tumor Assessments at Baseline): sites of diseases, number of disease sites per subject
- Target Lesions (Investigator Tumor Assessments at Baseline): Presence of target lesions, site of target lesion, sum of product diameters of target lesions.

